12.5.6. COVID-19 (Amended: 15 June 2020)

COVID-19 is an infectious disease caused by severe acute respiratory syndrome coronavirus 2 (SARS-CoV-2). When reporting an AE (serious or non-serious as defined in Section 12.5.2) related to COVID-19 infection, the following verbatim terms should be used according to World Health Organisation (WHO) definition (Please refer to Appendix 9):

- *Suspected COVID-19 infection; or*
- *Probable COVID-19 infection; or*
- *Confirmed COVID-19 infection*

Information pertaining to COVID-19 infection should be recorded at the next scheduled visit as medical history on the COVID-19 specific eCRF.

(Amended: 15 June 2020)

12.5.7. Clinical laboratory parameters and other abnormal assessments qualifying as adverse events or serious adverse events

In absence of diagnosis, abnormal laboratory findings (e.g. clinical chemistry, haematology, urinalysis) or other abnormal assessments that are judged by the investigator to be clinically significant will be recorded as AE or SAE if they meet the definition of an AE or SAE (refer to sections 12.5.1 and 12.5.2). Clinically significant abnormal laboratory findings or other abnormal assessments that are present at baseline and significantly worsen following the start of the study will also be reported as AEs or SAEs. However, clinically significant abnormal laboratory findings or other abnormal assessments that are associated with the disease being studied, unless judged by the investigator as more severe than expected for the subject's condition, or that are present or detected at the start of the study and do not worsen, will not be reported as AEs or SAEs.

The investigator will exercise his or her medical and scientific judgement in deciding whether an abnormal laboratory finding or other abnormal assessment is clinically significant.

CONFIDENTIAL212340 (ZOSTER-073 EXT:041 Y4-10)
Protocol Amendment 1 Final**12.5.8. Events or outcomes not qualifying as adverse events or serious adverse events****12.5.8.1. Pregnancy**

Female subjects who are pregnant or lactating at the time of revaccination must not receive additional doses of study vaccine but may continue other study procedures at the discretion of the investigator.

While pregnancy is not considered an AE or SAE, any adverse pregnancy outcome or complication or elective termination of a pregnancy for medical reasons will be recorded and reported as an AE or a SAE.

Note: The pregnancy should always be recorded on electronic pregnancy report.

The following should always be considered as SAE and will be reported as described in sections [12.5.10.1](#) and [12.5.10.4](#):

- Spontaneous pregnancy loss, including:
 - spontaneous abortion, (spontaneous pregnancy loss before/at 22 weeks of gestation)
 - ectopic and molar pregnancy
 - stillbirth (intrauterine death of fetus after 22 weeks of gestation).

Note: the 22 weeks' cut-off in gestational age is based on WHO-ICD 10 noted in the EMA Guideline on pregnancy exposure [[EMA](#), 2006]. It is recognized that national regulations might be different.

- Any early neonatal death (i.e. death of a live born infant occurring within the first 7 days of life).
- Any congenital anomaly or birth defect identified in the offspring of a study subject (either during pregnancy, at birth or later) regardless of whether the fetus is delivered dead or alive. This includes anomalies identified by prenatal ultrasound, amniocentesis or examination of the products of conception after elective or spontaneous abortion.

Furthermore, any SAE occurring as a result of a post-study pregnancy AND considered by the investigator to be reasonably related to the study vaccine will be reported to GSK as described in section [12.5.10](#). While the investigator is not obligated to actively seek this information from former subjects, he/she may learn of a pregnancy through spontaneous reporting.

CONFIDENTIAL212340 (ZOSTER-073 EXT:041 Y4-10)
Protocol Amendment 1 Final**12.5.9. Detecting and recording adverse events, serious adverse events and pregnancies**

A Paper Diary (pDiary), hereafter referred to as Subject Diary, will be used in this study to capture solicited AEs. The subject should be trained on how and when to complete each field of the Subject Diary.

The subjects/subjects' LAR(s) be instructed to contact the investigator immediately should the subjects manifest any signs or symptoms they perceive as serious.

Subject Diary training should be directed at the individual(s) who will perform the measurements of AEs and who will enter the information into the Subject Diary. This individual may not be the subject/subjects' LAR(s), but if a person other than the subject/subjects' LAR(s) enters information into the Subject Diary, this person's identity must be documented in the subject's source record. Any individual that makes entries into the Subject Diary must receive training on completion of the Subject Diary at the time of the visit when Subject Diary is dispensed. This training must be documented in the subject's source record.

At each revaccination visit, a Subject Diary card will be provided to the subject or subjects' LAR(s). The subject or subjects' LAR(s) (or subject's caregiver) will be instructed to measure and record the oral body temperature, and any solicited local/general AEs (i.e. on the day of revaccination and during the next 6 days) or any unsolicited AEs (i.e. on the day of revaccination and during the next 29 days occurring after revaccination). The subject or subjects' LAR(s) (or subject's caregiver) will be instructed to return the completed Subject Diary card to the investigator at the next study visit.

- Collect and verify completed Subject Diary cards during discussion with the subject on Visit 4 (Month 25) and on Visit 5 (Month 26).
- Any unreturned Subject Diary cards will be sought from the subject through telephone call(s) or any other convenient procedure.
- The investigator will transcribe the collected information into the eCRF in English.

12.5.9.1. Time period for detecting and recording adverse events, serious adverse events and pregnancies

All AEs during 30 days following administration of each dose of study vaccine (from day of revaccination and 29 subsequent days) must be recorded into the appropriate section of the eCRF, irrespective of intensity or whether or not they are considered vaccination-related.

The time period for collecting and recording SAEs will begin at the first receipt of study vaccine at Visit 3 (Month 24) during revaccination phase and will end at Visit 6 (Month 37) for each subject (See section [12.5.10](#) for instructions on reporting of SAEs). However, any SAEs assessed as related to study participation (e.g. study treatment, protocol-mandated procedures, invasive tests, or change in existing therapy) or related to

CONFIDENTIAL212340 (ZOSTER-073 EXT:041 Y4-10)
Protocol Amendment 1 Final

a GSK product will be recorded from the time a subject consents to participate in the study until the subject is discharged from the study.

SAEs that are related to the study vaccine administered during revaccination phase will be collected and recorded from the time of the first receipt of study vaccine at Visit 3 (Month 24) until the subject is discharged from the study or until the end of the study (See section [12.5.10](#) for instructions on reporting of SAEs).

All AEs/SAEs leading to withdrawal from the study will be collected and recorded from the enrollment visit [Visit 1 (Day 1)] up to the last study visit [Visit 7 (Month 49)].

After informed consent is obtained, the following events that occurred since the primary follow-up study ZOSTER-041 ***last study visit (Month 13) up to study ZOSTER-073 Visit 1 (Day 1)***, will be collected retrospectively ***and recorded in the medical history***:

- ***all SAEs related to the study vaccine***
- ***all suspected renal allograft rejections***
- ***all biopsy-proven renal allograft rejections***
- ***all suspected episodes of HZ considered as SAEs***
- ***all clinically-confirmed episodes of HZ considered as SAEs***

(Amended: 15 June 2020)

In addition to the above-mentioned reporting requirements and in order to fulfil international reporting obligations, SAEs that are related to study participation (i.e. protocol-mandated procedures, invasive tests, a change from existing therapy) or are related to a concurrent GSK medication/vaccine will be collected and recorded from the time the subject consents to participate in the study until she/he is discharged from the study.

The time period for collecting and recording pregnancies will begin at Visit 1 (Day 1) and will end at the last study visit [Visit 7 (Month 49)]. See section [12.5.10](#) for instructions on reporting of pregnancies.

The time period for collecting and recording of pIMDs will begin at the first receipt of study vaccine at Visit 3 (Month 24) during revaccination phase and will end at Visit 6 (Month 37), approximately 12 months following administration of the last revaccination dose. See section [12.5.10.5](#) for instructions on reporting of pIMDs.

The time period for collecting and recording of biopsy-allograft rejections will begin at the enrollment visit [Visit 1 (Day 1)] and will end at the last study visit [Visit 7 (Month 49)]. See section [12.5.10.5](#) for instructions on reporting of renal allograft rejection.

The time period for collecting and recording of IMCs (including HZ) will begin at the enrollment visit [Visit 1 (Day 1)] and will end at the last study visit [Visit 7 (Month 49)]. See section [12.5.10.5](#) for instructions on reporting of HZ.

CONFIDENTIAL

212340 (ZOSTER-073 EXT:041 Y4-10)

Protocol Amendment 1 Final

Of note, any medical events that occurred since the ZOSTER-041 last study visit (Month 13) up to study ZOSTER-073 Visit 1 (Day 1) will be recorded in medical history section on the eCRF and should not be reported via expedited reporting.
(Amended: 15 June 2020)

Evaluation of adverse events and serious adverse events

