4. OBJECTIVES AND ENDPOINTS

The study objectives and endpoints are presented in [Table 5](#).

Table 5 Study objectives and endpoints (Amended: 15 June 2020)

Objectives	Endpoints
Primary	
LTFU phase - Immunogenicity assessment • To evaluate persistence of humoral immunity after primary vaccination course.	In all subjects: • Anti-gE antibody concentrations as determined by ELISA at Day 1, Month 12 and Month 24.
Revaccination active phase - Immunogenicity assessment • To evaluate humoral immunity of HZ/su vaccine post-revaccination Doses 1 & 2.	In all subjects: • Anti-gE antibody concentrations as determined by ELISA at pre-revaccination (Month 24) and at 1-month post-revaccination Dose 1 (Month 25) and Dose 2 (Month 26).
Secondary	
LTFU phase - Immunogenicity assessment • To evaluate persistence of cellular immunity after primary vaccination course.	In CMI sub-cohort: • Frequencies of gE-specific CD4+ T-cells expressing two or more markers such as IFN-γ, IL-2, TNF-α, CD40L as determined by ICS at Day 1, Month 12 and Month 24.
LTFU phase - safety assessment • To evaluate safety of HZ/su vaccine from the study ZOSTER-041 last visit to study ZOSTER-073 Visit 3.	In all subjects: • Related-SAEs 
– Occurrence of SAEs related to primary vaccination as assessed by the investigator from the study ZOSTER-041 last visit (Month 13) to study ZOSTER-073 Visit 3 (Month 24). • HZ episodes 
– Occurrence of suspected or confirmed HZ cases from the study ZOSTER-041 last visit (Month 13) to study ZOSTER-073 Visit 1 (Day 1).– Occurrence of confirmed HZ cases from Day 1 through Month 24.

CONFIDENTIAL

212340 (ZOSTER-073 EXT:041 Y4-10)

Protocol Amendment 1 Final

Objectives	Endpoints

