5. STUDY DESIGN

5.1. Scientific rationale for study design

This study will evaluate the persistence of gE-specific immunogenicity after the primary 2-dose HZ/su vaccination in study ZOSTER-041 and the effect on immunogenicity and safety of revaccination with two additional doses of HZ/su vaccine after approximately 7 years in ZOSTER-041 in RT subjects taking daily CIS therapy. Study ZOSTER-073 will provide insights into HZ/su-induced immune responses in the RT population and, potentially, in other immunocompromised populations including SOT, AID, IID subjects receiving CIS.

Former study ZOSTER-041 subjects who received two doses of HZ/su vaccine will be offered enrollment into study ZOSTER-073 at participating centers.

Study ZOSTER-073 has three distinct phases:

- In the long-term follow-up (LTFU) phase, subjects will be followed for two years* (Day 1 to Month 24). Over the same time period, the occurrences of confirmed HZ cases and biopsy-proven RT rejections will be prospectively collected. Whereas, the occurrences of confirmed/suspected HZ cases; and RT rejections will be retrospectively collected back to subjects' study ZOSTER-041 last visit. **(Amended: 15 June 2020)**

** Subjects who are ineligible for revaccination or unwilling to receive revaccination (hereafter referred to as non-revaccinated subjects, see [Glossary of terms](#)) will be invited to be followed in an extension of the LTFU phase for a total of 4 years (Day 1 to Month 49), with safety and immunogenicity assessments at Months 37 and 49.*

- In the revaccination active phase (Months 24 through 26), subjects will receive two additional doses of HZ/su vaccine, administered on a 1 to 2-month apart schedule at Months 24 and 25. Safety and immunogenicity assessments will be performed 1 month post-revaccination Doses 1 and 2 at Months 25 and 26, respectively.
- In the revaccination follow-up phase (Month 26 to study end), safety and immunogenicity following revaccination will be prospectively monitored at Months 37 and 49 (i.e. 12 and 24 months post-revaccination Dose 2).

In study ZOSTER-073, the occurrence of HZ episodes will be collected and confirmed by molecular biology tests (HZ PCR testing) and the HZ Ascertainment Committee (HZAC) decision (see section [12.2.2](#) for details).

CONFIDENTIAL

212340 (ZOSTER-073 EXT:041 Y4-10)

Protocol Amendment 1 Final

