7.6. **Intercurrent medical conditions that may lead to elimination of a subject from per-protocol analyses**

At each study visit, it must be recorded if the subject has experienced or is experiencing any intercurrent medical condition (IMC) that may lead to elimination from per protocol analysis. If it is the case, the condition(s) must be recorded in the eCRF.

IMCs are clinical events occurring in the course of the study which might alter or confound the interpretation of the immunologic (not safety) assessments of the protocol. With regards to humoral gE assessments, this includes any clinical event that might increase or decrease the level of anti-gE antibodies, such as protein losing conditions in which the loss of gamma-globulin or total proteins might underestimate the subject's gE response (e.g. protein loss conditions associated with proteinuria). Additional examples would be conditions that would cause the administration of exogenous anti-gE antibodies, resulting in an overestimate the subject's anti-gE response, such as conditions requiring the use of immunoglobulin (IV Ig) or blood products. For the CMI assessments, IMCs would be active viral infections that may alter CD4+ T cell counts and/or responses. Examples, although not exhaustive, of such acute viral infections would include acute Hepatitis A, acute Hepatitis B, new onset human immunodeficiency virus (HIV), and potentially acute cytomegalovirus (CMV) and/or Epstein Barr virus (EBV) infections.

The occurrence of an episode of HZ is an IMC, as the anti-gE antibody formed during active shingles in response to reactivation of VZV cannot be distinguished from the anti-gE antibody formed in response to vaccination. At Visit 1, all subjects will be informed of the signs and symptoms of typical HZ, provided a HZ-specific diary card and ZBPI questionnaire, and instructed to call for an appointment if HZ develops. The reporting period for cases of HZ will be from enrollment visit to study end. HZ cases will be collected in HZ specific screen in the eCRF. Note that all suspected or confirmed HZ that occurred since the primary follow-up study ZOSTER-041 will be collected retrospectively as part of the medical history.

ZOSTER-073 IMCs will be reported either as AE or SAEs (as appropriate) in the eCRF from enrollment visit (Visit 1) up to study end (Visit 7).

7.7. **Contraindications to subsequent vaccine administration**

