8.1.3. Medical history

At the enrollment visit, obtain the subject's medical and vaccination history, since the last study ZOSTER-041 visit, by interview and/or review of the subject's medical records and record in the eCRF any pre-existing conditions or signs and/or symptoms present in a subject prior to the study start.

CONFIDENTIAL212340 (ZOSTER-073 EXT:041 Y4-10)
Protocol Amendment 1 Final

The following medical conditions, medication(s)/product(s)/vaccine(s) will be collected and recorded:

- Chronic disorders (e.g. diabetes mellitus, chronic obstructive pulmonary disease, stroke, cardiovascular disorders, gout).
- pIMDs.
- HZ (suspected or confirmed).
- Allograft rejection(s) (suspected or biopsy-proven).
- Medications/products/vaccines (except vitamins and dietary supplements) being taken within 1 month (30 days) before the enrollment visit.
- Any immunoglobulins and blood or blood products administered at and within for 90 days before enrollment visit.
- Any long-acting immune-modifying drugs administered at and within 360 days before enrollment visit (e.g. infliximab).
- Any use of anti-CD20 or other B-cell monoclonal antibody agents (e.g., rituximab, ocrelizumab) administered at and within 360 days before enrollment visit.

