8.4.8. Evaluation and confirmation of suspected HZ cases**8.4.8.1. Suspected Herpes Zoster**

Suspected HZ is defined as a new rash characteristic of HZ (i.e. unilateral, dermatomal and accompanied by pain broadly defined to include allodynia, pruritus or other sensations), or a vesicular rash suggestive of VZV infection regardless of the dermatomal distribution and without alternative diagnosis.

Additionally, sometimes HZ cases do not present with the characteristic HZ or VZV rash, but have a clinical presentation and specific laboratory findings* suggestive of VZV infection. These cases should also be considered as occurrences of HZ.

* Specific laboratory findings include VZV-positive polymerase chain reaction (PCR) culture, immunohistochemistry, or other tests that strongly suggest VZV-infection, which have been performed in the course of a medical evaluation.

A suspected case of HZ is to be evaluated in the clinic by the investigator, within days of onset, ideally while vesicles or ulcerations are present.

Complications of HZ include, but are not limited to, PHN, HZ vasculitis, disseminated disease, ophthalmic disease, neurologic disease, and visceral disease.

The occurrence of HZ and/or HZ complications will constitute an AE/SAE, as appropriate. The occurrence of HZ is also an intercurrent medical condition (IMC) (see section 7.6).

CONFIDENTIAL

212340 (ZOSTER-073 EXT:041 Y4-10)
Protocol Amendment 1 Final

The reporting period for events of HZ will be from Visit 1 (Day 1) to study end (Month 49). At Visit 1, all subjects will be informed of the signs and symptoms of typical HZ.

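### Protocol 12.5.9.1 restricts retrospective gap-period HZ collection to serious episodes, in conflict with the endpoint and with 5.1, 7.6 and 8.1.3, so non-serious HZ could be omitted

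*Protocol*

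**What the plan says.** Protocol 12.5.9.1 lists five kinds of event to be gathered retrospectively after consent, for the period from the last ZOSTER-041 visit (Month 13) to ZOSTER-073 Visit 1. The two HZ items are "all suspected episodes of HZ considered as SAEs" and "all clinically-confirmed episodes of HZ considered as SAEs". The rejection items beside them carry no seriousness limit; one reads simply "all suspected renal allograft rejections".

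Four other places address HZ in the same window without a seriousness limit:

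- Table 5, secondary safety endpoint: "Occurrence of suspected or confirmed HZ cases from the study ZOSTER-041 last visit (Month 13) to study ZOSTER-073 Visit 1 (Day 1").
- Section 5.1: "the occurrences of confirmed/suspected HZ cases; and RT rejections will be retrospectively collected back to subjects' study ZOSTER-041 last visit".
- Section 7.6: "all suspected or confirmed HZ that occurred since the primary follow-up study ZOSTER-041 will be collected retrospectively as part of the medical history".
- Section 8.1.3, items to record at enrollment: "HZ (suspected or confirmed").

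The Visit 1 medical-history row of the Schedule of Activities names HZ cases, requires eCRF documentation and points to 8.1.3. Near its end, 12.5.9.1 itself adds that any medical event in the gap goes into the medical history section of the eCRF and not through expedited reporting.

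The SAP uses these data without a seriousness filter. Section 4.3.2.1 tabulates subjects with suspected or confirmed HZ in the gap, with exact 95% CIs. Section 4.5.3.4 lists the episodes. Elimination code 2060 (section 3.1) cites clinically diagnosed suspected HZ before Visit 1.

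**The concern.** Section 8.4.2 sends sites to 12.5.9.1 for the periods over which safety information is recorded, so a reader would take that list as the governing rule. Read alone, it excludes every HZ episode not judged serious, although the endpoint counts such episodes.

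Three outputs depend on complete capture:

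- The gap-period HZ count and percentage in SAP 4.3.2.1.
- The endpoint on allograft function around HZ episodes, which covers the period from ZOSTER-041 Month 13 to ZOSTER-073 Month 24 and can use only recorded episodes.
- The per-protocol set for persistence. Section 7.6 explains that antibody produced by an HZ episode cannot be told apart from antibody due to vaccination, and code 2060 exists to remove affected visits. It cannot act on an episode that nobody recorded.

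**Working it through.** **Does the qualifier restrict anything?** It would be harmless if every HZ episode were an SAE by definition. Section 8.4.8.1 says otherwise: "The occurrence of HZ and/or HZ complications will constitute an AE/SAE, as appropriate". HZ may be serious or not, so the list in 12.5.9.1 is narrower than the endpoint.

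**Could the list be read as non-restrictive?** If the later sentence on gap-period medical events is a collection rule, it already covers non-serious HZ and the qualified bullets conflict with it inside one section. If it only says where collected events are entered, the bullets stand as a restriction and conflict with Table 5, 5.1, 7.6 and 8.1.3. The text is inconsistent either way.

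**Scale.** The plan states no expected number of gap-period HZ cases, so there is no figure to reproduce. The following is illustrative.

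Inputs:

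- Subjects: 68 (SAP 1.2, Table 1, actual number).
- Gap: Visit 1 is about 4 to 5 years after the last primary dose (Schedule of Activities), and ZOSTER-041 Month 13 is 12 months after dose 2 (SAP 1.2). The gap is therefore about 3 to 4 years. SAP 1.2 also provides for first visits assigned to year 6, so some gaps may be longer.
- HZ incidence in renal transplant recipients: 24.4 and 28 per 1000 person-years, from two cohorts in Protocol 3.2.2. The 22.2 given there for one of these cohorts is for all solid organ transplants and is not used.
- Vaccine effect: none, or 68% as reported in Protocol 3.1 for autologous stem-cell transplant recipients. Applying that figure here is an assumption.

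Expected cases = subjects × years × rate, multiplied by (1 − 0.68) = 0.32 where efficacy is assumed.

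| Gap | Person-years | Rate per 1000 | No vaccine effect | With 68% efficacy |
|---|---|---|---|---|
| 3 years | 68 × 3 = 204 | 24.4 | 4.98 | 1.59 |
| 3 years | 204 | 28 | 5.71 | 1.83 |
| 4 years | 68 × 4 = 272 | 24.4 | 6.64 | 2.12 |
| 4 years | 272 | 28 | 7.62 | 2.44 |

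The ranges are about 5.0 to 7.6 and about 1.6 to 2.4 cases.

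The Clopper-Pearson 95% limits, the method in SAP 4.1.1, are the 0.025 quantile of Beta(x, n − x + 1) and the 0.975 quantile of Beta(x + 1, n − x). With n = 68:

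| Subjects with HZ | Percentage | Exact 95% CI |
|---|---|---|
| 0 | 0% | 0 to 5.3 |
| 1 | 1.5% | 0.0 to 7.9 |
| 2 | 2.9% | 0.4 to 10.2 |
| 5 | 7.4% | 2.4 to 16.3 |

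If two subjects truly had HZ, missing one halves the percentage and missing both gives a report of no cases.

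**The case against.** The strongest reply is that the qualifier is an isolated slip in an adverse-event appendix and that the working instructions are clear. The schedule row used at Visit 1 names HZ cases and leads to 8.1.3, which asks for suspected or confirmed HZ. Sections 5.1 and 7.6 agree, and 12.5.9.1 itself directs all gap-period medical events to medical history. A site following any of these would record non-serious HZ. This stands: the documents show a route to loss, not loss itself.

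The scale figures are also open to challenge. The incidence rates are for the period following transplantation, and one cohort's mean onset in renal recipients was 15.5 months. These subjects are years past primary vaccination, so the rates may not carry over. That is a reason to treat the counts as illustrative. It does not remove the contradiction, which needs no rate.

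Two stronger readings are tempting. A reader might infer that sites would lose most of their HZ cases. The documents do not give the share of HZ episodes that are serious, and such a loss would also require sites to ignore 8.1.3 and the later sentence in 12.5.9.1. A reader might also infer that the omission makes the vaccine look more protective. The study assesses no efficacy (Protocol 8.2), has no control group (5.2) and tests no hypothesis (SAP 2.1). What could be understated is a descriptive safety count. Code 2060 removes only the visits concerned, so an unrecorded episode need not affect every persistence timepoint.

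**Conclusion.** The contradiction is in the current protocol text and should be corrected. Both HZ items in 12.5.9.1 are limited to serious episodes, while the endpoint, sections 5.1, 7.6 and 8.1.3, and the SAP analyses that use the data are not. Omission of non-serious episodes is a risk and not a certainty.

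The point is minor, but the analysis has little tolerance for missing cases. Under the stated assumptions the expected number is between about 1.6 and 7.6, so one or two omissions would visibly change the reported percentage. That conclusion rests on the 68 enrolled subjects, a 3 to 4 year gap, incidence borrowed from other renal transplant cohorts, and either no vaccine effect or an efficacy taken from a different population.

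**What to change.** Remove the SAE qualifier from both HZ items in 12.5.9.1, or add a sentence stating that the list does not limit what 8.1.3 requires.

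New wording cannot change how Visit 1 was carried out. The SAP (12 March 2024) describes enrollment in the past tense and reports 68 actual subjects. Before the final analysis, therefore, ask each site to confirm against source records that non-serious HZ between the last ZOSTER-041 visit and Visit 1 was entered in medical history. Add any missing episodes, apply code 2060 to them during the data management review, and disclose any remaining shortfall in the clinical study report.

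The cost is a wording change and one small data query covering at most 68 subjects. No new visit, sample or procedure is needed.
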